## **2. Objectives**

The objectives of this clinical study are to evaluate:

- The effectiveness of treatment of cavitated caries in children by application of silver diamine fluoride (SDF) in comparison to conventional restorative treatments
- The perceptions of parents and patients to both treatment modalities and their levels of acceptability
- The opinions of dental providers in terms of ease of use and clinical time spent
- The relative cost-effectiveness of the two treatment approaches regarding both practitioner chair time and material-based cost

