### **4.2. General Outline**

Children, 2-10 years of age will be invited to participate. The original study site is Mott Children's Health Center (MCHC) in Genesee County, Michigan. Following a slow recruitment period, the University of Michigan School of Dentistry (UMSOD) Children's Clinic was added as a second study site. Given the current data in the literature, the combined failure rate for conventional restorative techniques (e.g. compomers) is approximately 29% at one year follow-up, while application of silver diamine fluoride has a failure rate of 63% at one year follow-up, with increased success over time. Although the failure rate of SDF at one-year follow-up seems alarming, as indicated by Zhi, *et al.* it may be possible to increase the success rate with additional applications providing success rates up to 90.1% at 24 months. Using these data,  $\alpha$ -value of 0.05 and a Power set at 80%, the resulting sample size would be 68 (34 per group) as calculated using the software, nQuery (Appendix 1). To account for 30% attrition, the final number needed for the initial study will be 98 (92 for 25% attrition, 86 for 20% attrition). Subjects will be contacted by phone regularly and invited to two intermediate clinic visits (plus a final study visit) to reduce attrition (Table 1). Given a review of the current literature of the few Randomized Controlled Clinical Trials involving SDF worldwide, the majority of this research has been completed with pre-school aged children. Almost all research discusses arresting or prevention of caries in the

primary dentition, as well as prevention of caries on first permanent molars. Due to the strength of the current research, this study will be focused on the primary dentition of children in the U.S. These children and their parents will be approached when presenting for examination/recall/or treatment at Mott Children's Health Center, Flint, MI, or the University of Michigan School of Dentistry Children's Clinic, Ann Arbor, MI. Interested families with children that qualify following screening examination will be provided with an *Informed Consent/Assent* (Appendix 3) and an *Enrollment Information Form* (Appendix 4).

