## 6. Study Visits and Intermediate Contacts

Recalls for both groups will occur via phone questionnaire as well as follow-up visits. Participants will be contacted at 1 month, 2 months, 4.5 months and 9 months ( $\pm$  2 weeks) following restoration placement or application of SDF. Subjects will need to present to the clinic for follow-up visits at 3 months ( $\pm$  6 weeks), 6 months ( $\pm$  6 weeks), and for study completion at 12 months ( $\pm$  6 weeks) (Table 1). Subjects will also be called to schedule and confirm these follow-up visits; these short calls will require no payment to the study subjects. In the case of an emergency, an emergency visit will be scheduled at Mott Children's Health Center or the University of Michigan School of Dentistry. An emergency will be evaluated and treated according to the AAPD guidelines, followed by completion of appropriate case report forms (CRFs) and reporting to IRBs and study sponsors (Appendix 10, CRF 14-17). In the event of minor or major failure in either study group, the subject will be withdrawn from the study and teeth will be given the appropriate treatment as stated in the AAPD Guidelines free of charge, these teeth will be categorized as a failure, and a *CRF 04 Treatment Deviation CRF (Appendix 10, CRF 04)* will be completed.

**Table 1.** Patient Contact Interval

Patient Contact	Recall Interaction	Time Scale
Clinic Visit #1	Consent/Accent, baseline questionnaires, initial caries assessment, radiographs*, intervention	T = 0
Intermediate Contact	Attrition prevention, update contact information, follow-up on pain	T = 1 month, 2 months (Additional reminder for Clinical Visit #2)
Clinic Visit #2	Assessment for major and minor failure & assessment of pain and parent satisfaction	T = 3 months
Intermediate Contact	Attrition prevention, update contact information, follow-up on pain	T = 4.5 months (Additional call reminder for Clinical Visit #3)
Clinic Visit #3	Reapplication of SDF in that group; Assessment for major & minor failure, radiographs*, and assessment of pain and parent satisfaction	T = 6 months

Intermediate Contact	Attrition prevention, update contact information, follow-up on pain	T = 9 months (Additional call for scheduling/reminder for Clinical Visit #4)
Clinic Visit #4	Assessment for major & minor failure, radiographs*, and final questionnaires	T = 12 months

\* Radiographs will be obtained only if an existing radiograph within 30 days of the visit is not available.

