## 7. Study Outcomes

### 7.1. Questionnaires + Acceptability Measures

At the baseline clinical visit:

- *Pediatric Medical History Form*
  - Mott Children's Health Center/University of Michigan School of Dentistry Children's Clinic standard form
- *CRF 05 Baseline Parent Questionnaire* (Appendix 10, CRF 05)
- *CRF 06 Child Questionnaire* (Appendix 10, CRF 06)

When scheduled intermediate contact occurs via phone (or in person if presenting to MCHC/UMSOD for other reasons) at 1, 2, 4.5, and 9 months, the following form will be completed by the personnel making the contact, documenting the answers provided by the parent:

- *CRF 07 Intermediate Contact* (Appendix 10, CRF 07)

At recall visits (3 & 6 months, 12 month final recall, plus emergency visits) the parent and patient will complete:

- *CRF 08 Follow-up Parent Questionnaire* (Appendix 10, CRF 08)  
OR
- *CRF 09 6 & 12 Month Parent Questionnaire* (Appendix 10, CRF 09)
- *CRF 06 Child Questionnaire* (Appendix 10, CRF 06)

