## **10. Statistical Analysis**

Power of the study will be fixed at 80% ( $\beta=0.20$ ) just as was used in calculation for necessary sample size, with  $\alpha = 0.05$  as the significance level. Data will be entered into SPSS Statistics or

another secured data collection system and data will be analyzed. Information will be stored on a password protected computer using an encrypted file and will be maintained as confidential protected health information (PHI). Examiners will be trained at the start of the study and calibrated on the use of the ICDAS criteria, and on the clinical outcome variables using extracted teeth to determine intra and inter-examiner reliability (dentin color, dentin hardness, and lesion size in mm), which will be measured with kappa statistics. A Chi-square test will be applied to determine if there is a difference in distribution of variables such as age, gender, brushing habits, fluoride exposure, etc. Chi-square tests will also be used to determine differences in dropout rates, failure rates, patient satisfaction/acceptance, and overall cost. The primary outcome, the proportion of children reporting major failures during the 12 month follow up period, will be analyzed using a mixed model with a binomial error structure. We will also analyze minor failures in a similar manner. The dependent variables will be a binary indicator of major failure, with differences between study treatments fitted as fixed effects. Estimates of the relative risk of major failure in the two groups will be presented in the form of odds ratios and associated 95% confidence intervals. Within this framework we will be able to estimate:

1. The mean difference between groups at the end of the follow up period;
2. The mean difference between groups across the whole of the follow up period; and
3. The difference in the rate of change of the outcome across the follow up period

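### Satisfaction and acceptance are collected at three follow-up visits, but the only planned analysis is a chi-square test, which gives no effect estimate, ignores any answer order and cannot use the repeats

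*Combined protocol and SAP*

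**What the plan says.** Section 2 makes acceptability the second of four objectives: "The perceptions of parents and patients to both treatment modalities and their levels of acceptability".

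The data are repeated. Section 7.1 states: "At recall visits (3 & 6 months, 12 month final recall, plus emergency visits) the parent and patient will complete", followed by the parent and child forms. Table 1 in Section 6 agrees:

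- 3 months: "Assessment for major and minor failure & assessment of pain and parent satisfaction"
- 6 months: the visit also includes "and assessment of pain and parent satisfaction"
- 12 months: "Assessment for major & minor failure, radiographs*, and final questionnaires"

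Section 10 gives the analysis in one sentence: "Chi-square tests will also be used to determine differences in dropout rates, failure rates, patient satisfaction/acceptance, and overall cost". It names no visit, response grouping, effect measure or interval for this outcome.

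The same section has a fuller framework, but only for failures. The primary outcome, major failure, "will be analyzed using a mixed model with a binomial error structure. We will also analyze minor failures in a similar manner". Odds ratios, 95% confidence intervals and differences over follow-up are promised inside that framework. Satisfaction is not part of it.

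**The concern.** Three features of the planned test do not fit the outcome.

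1. **No estimate.** A chi-square test yields a p-value. It does not show which arm families find more acceptable, or by how much, which is what the objective asks.
2. **No use of order.** If answers are graded, the test treats the grades as unlabelled categories and spreads its power over several degrees of freedom.
3. **No place for repeats.** The test assumes one independent answer per child. With three visits the analyst must pool forms (invalid), choose one visit (discards data) or test each visit (multiplicity). The plan does not choose, so the choice could be made after the data are seen.

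Acceptance is one of the study's main aims (Section 3.6), so a weak or ambiguous analysis here would leave one of its central questions poorly answered.

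**Working it through.** **Sample sizes used.** The documents give no power for satisfaction, so I take the numbers per arm from the failure calculation in Section 4.2 (29% v 63%, alpha 0.05, power 80%; two-sided assumed, because sidedness is not stated). With pooled variance:

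n = (1.960 + 0.842)² × 2 × 0.46 × 0.54 / 0.34² = 33.7, so 34 per arm, as stated. With 30% attrition, 34/0.70 = 48.6, so 49 per arm and 98 in total, also as stated.

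The checks below use 34 and 49 per arm.

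**Cost of ignoring order, one visit.** The forms are in Appendix 10, which is not in the reviewed text, so the scale is assumed. I simulated the Pearson chi-square test against the rank-sum test (4,000 replicates) under a proportional-odds shift toward the upper end. Relative loss = 1 − (chi-square power / rank-sum power).

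| Assumed answers | Odds ratio | n per arm | Chi-square | Rank-sum | Relative loss |
|---|---|---|---|---|---|
| Five levels, 5/10/20/35/30% | 2.5 | 34 | 31% | 52% | 40% |
| | 2.5 | 49 | 45% | 67% | 33% |
| | 3 | 34 | 42% | 66% | 36% |
| | 3 | 49 | 61% | 83% | 27% |
| Three levels, 15/35/50% | 2.5 | 34 | 37% | 46% | 20% |
| | 2.5 | 49 | 52% | 62% | 16% |
| | 3 | 34 | 48% | 59% | 18% |
| | 3 | 49 | 65% | 75% | 12% |
| Yes/no | either | either | equal | equal | none |

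Type I error is about 4-6% for both tests. Other distribution shapes at the same odds ratios and sizes gave losses of 11-30% with three levels and 23-47% with five.

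An analytic check agrees. At the noncentrality that gives a 1-df ordered test 80% power (2.802² = 7.85), the Pearson test has 71% power with three levels and 60% with five. The relative losses are 9/80 = 11% and 20/80 = 25%.

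**Pooling three visits as independent.** In simulations with no true difference and a within-child correlation of 0.3, 0.5 or 0.7 on an underlying continuous scale, nominal 5% tests rejected as follows:

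- five-level item: 8.7%, 12.3% and 18.3%
- yes/no item: 10.6%, 14.3% and 18.4%

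If the correlation is instead taken on the yes/no answers themselves, the variance inflates by 1 + 2ρ = 1.6, 2.0 or 2.4. The effective critical value falls to 1.96/√1.6 = 1.55, 1.96/√2.0 = 1.39 or 1.96/√2.4 = 1.27, giving about 12%, 17% and 21%.

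**Testing visits singly.** Three tests at 5% give a family-wise error of up to 1 − 0.95³ = 14.3% if independent, and less if correlated. Using one visit only gives up a precision factor of 3/(1 + 2ρ) = 1.88, 1.50 or 1.25. If a three-visit analysis with complete data had 80% power, one visit would have Φ(2.802/√factor − 1.960) = 53%, 63% or 71%.

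**Who is left at 12 months.** Section 6 withdraws a child at any minor or major failure. Section 4.2 expects 63% failure with SDF and 29% with conventional care. If every failure were found before the 12-month visit and ended the questionnaires, the children remaining before other dropout would be:

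- of 49 per arm: 49 × 0.37 = 18 v 49 × 0.71 = 35
- of 34 per arm: 34 × 0.37 = 13 v 34 × 0.71 = 24

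These are extremes, since failures first found at 12 months could still yield a form.

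**The case against.** - **The scale is unknown.** The word for levels in Section 2 is ordinary prose and does not establish a graded item. This stands. A reader might infer that the planned test loses about a third of the power, but that needs an assumed five-level scale and effect size. With yes/no items the loss from order is nil. The figure would also say nothing about repeats, because the simulation covers one visit.
- **The plan does not say it pools visits.** This also stands. The inflated type I error is a consequence of one permitted reading and is not a stated intention.
- **Chi-square is not always the weaker test.** Section 3.4 reports that black staining displeases some people, although it adds that satisfaction did not fall. If answers polarised, for example 5/10/20/35/30% against 25/10/5/15/45% (an assumed illustration), chi-square has about 80% power and rank-sum about 6-7% at 34 per arm. A reader might call chi-square the weakest reasonable choice; this example shows that it need not be.
- **A joint model may not be possible for every item.** Section 7.1 lists two parent forms, CRF 08 or CRF 09 (the 6- and 12-month form), so the 3-month parent items may differ. Only the child form, CRF 06, is plainly the same throughout. This limits the remedy to items that are repeated.
- **This is not the primary outcome, and no stated figure is contradicted.** That is correct and bears on priority. The lack of an estimate, a named visit and a method for repeats remains.

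**Conclusion.** The point holds, and its core needs no assumption: chi-square is the only method named for satisfaction and acceptance, the questionnaires recur at three scheduled visits, and no visit, effect estimate, interval or handling of repeats is given. The plan already uses a more suitable framework for failures.

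The size is conditional. For proportional-odds shifts of 2.5-3 at one visit with 34-49 per arm, ignoring order costs nothing for a yes/no item, roughly 15-20% of the power with three levels (12% in the mildest case tabulated) and about 25-40% with five. Other answer distributions widen these ranges, and polarised answers can reverse the comparison. Pooling visits as independent would put type I error at about 9-18% for correlations of 0.3-0.7 on the underlying scale.

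A single 12-month comparison, even with an ordered test, would not be a sufficient remedy. Under the withdrawal rule it would mainly compare non-failures, in unequal numbers by arm.

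**What to change.** Amend Section 10 so that satisfaction and acceptance are taken out of the chi-square sentence and analysed as follows:

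1. State the response scale of each item and the visits at which the identical item is asked. Analyse parent and child items separately.
2. Fit a repeated-measures model with child as the cluster: proportional-odds for ordered items and logistic for yes/no items. Use all scheduled visits that share the item, with treatment, visit and their interaction.
3. Report an odds ratio with 95% CI by visit and overall, and name in advance which one is the main result.
4. Keep every answer given before withdrawal at failure. State how missing later answers are handled, since they depend on outcome and will probably be unequal by arm.
5. Check proportional odds and show the full response distribution by arm and visit, so that polarised answers are visible.
6. State whether forms from emergency visits are included.

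The cost is SAP wording and slightly more analysis work, with no new data. The downside is the proportional-odds assumption, which can lose power if answers polarise; item 5 is there to show whether that has happened.

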### **3.5. Silver Diamine Fluoride Variations in Application**

While much of the previously presented research suggests that there are potential positive effects of SDF, there are still many potential variations in regimens for application. Many would assume that for effective arrest of caries, it would be important for carious debris to be removed reducing the bacterial load. However, it has been shown that caries removal did not offer any significant beneficial effect in terms of arresting carious lesions and only showed a reduction in the number

of arrested lesions that turned black in the NaF group, as 100 percent of the lesions in the SDF group presented with a black coloration regardless of caries removal. For this reason, it has been suggested that caries removal would be unnecessary, which would make the procedure more simple and could increase the potential for patient acceptability which is important because it is one of the advantages of this product.

Many studies have shown a variation in number of applications and concentrations, leading to the research question of determining an exact regimen. In terms of concentration, when observed at 6 months, it was noted that a single application of 38 percent SDF could arrest caries in comparison to 12 percent SDF, which could not. Regarding the optimal number of applications, it was shown that an annual topical application of 38 percent SDF would arrest 37 percent of caries at 12 months and up to 79.2 percent of caries at 24 months, while biannual applications resulted in 53 percent arrested caries at 12 months and 90.7 percent arrested caries at 24 months.

Due to the potentially highly positive caries arrest effects of SDF, research has been conducted in an attempt to prevent washing away of the product when placed on the tooth surface. It has been postulated that if the treated surface was to turn instantaneously black, this would indicate that the process had been accelerated and was in turn more effective. Studies have shown that applications of 10% stannous fluoride or tannic acid were not shown to have an additional benefit in arresting caries although they may have appeared to accelerate the process of SDF uptake by the tooth surface.

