### **5.2. SDF management of caries**

- The selected tooth with notable decay into dentin will be isolated with cotton rolls.
- No caries removal will be performed, except for food or other obvious debris.
- Tooth will be dried with gauze and SDF solution will be placed on the carious dentin until it is saturated.
- Excess SDF will be blotted dry with a cotton pellet.
- A second application of SDF solution will then be placed to ensure that the entire carious surface is wetted, and excess will again be blotted with a cotton pellet.
- Following the second application of SDF, the area will be isolated for 3 minutes to allow for ample drying before allowing contact with saliva and soft tissues
- Should the SDF come in contact with any soft tissues, soft tissue should immediately be wiped with a saline wipe
- Following completion of the SDF intervention visit, the provider will complete the CRF 03 *Intervention Visit: Silver Diamine Fluoride* CRF (Appendix 10, CRF 03).
- A second application of SDF will be applied at 6 month recall, following the same protocol as noted above (Due to the potential for increased caries arrest rate with a 6 month application).
- Any new carious lesions that develop after the initial treatment will be recorded, and treated using conventional treatment methods and will not be included in the study.
- Following the completion of this study, teeth in the SDF group will be treated according to AAPD guidelines or observed for exfoliation. The parent of an SDF treated child can elect a restoration following AAPD guidelines at the 12 month visit.

Both groups will receive the following, according the standard procedures at the MCHC/UMSOD:

- Oral Health Instruction (OHI) and diet instruction
- Tooth brushing/dentifrice use at home
- Fissure sealants for permanent teeth will be placed if deemed necessary.
- Traditional preventative care at recalls based on AAPD guidelines (Regular recall exams, prophylaxis, scaling, flossing, and fluoride varnish at 6 month recalls will be provided for both treatment arms. Special care will be taken to not apply fluoride varnish directly to the carious lesion which is being treated with SDF.)

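### The 80% power was calculated for 29% combined failure against 63% non-arrest, but the primary outcome is major failure alone, for which no rate or power is given

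*Combined protocol and SAP*

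**What the plan says.** Section 10 defines the primary endpoint as "The primary outcome, the proportion of children reporting major failures during the 12 month follow up period", to be analysed with a binomial mixed model. Minor failures get a separate analysis. The same section fixes power at 80% with alpha 0.05, "just as was used in calculation for necessary sample size".

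That calculation is in Section 4.2. For restorations it assumes that "the combined failure rate for conventional restorative techniques (e.g. compomers) is approximately 29% at one year follow-up". For SDF it assumes that "application of silver diamine fluoride has a failure rate of 63% at one year follow-up". From these it obtains 34 per group (68 in total), raised to 98 for 30% attrition.

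Section 3.5 shows where the SDF figure comes from: "an annual topical application of 38 percent SDF would arrest 37 percent of caries at 12 months", and 100% − 37% = 63%. It also reports that "biannual applications resulted in 53 percent arrested caries at 12 months". Section 5.2 plans that "A second application of SDF will be applied at 6 month recall".

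For SDF teeth, Table 2 (Section 7.2) puts soft dentin and lesion growth under minor failure. Major failure is limited to pulpitis that needs a pulpotomy or extraction, an abscess, or a tooth that has become unrestorable. Section 6 adds: "In the event of minor or major failure in either study group, the subject will be withdrawn from the study".

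**The concern.** The sample size and the primary analysis rest on different endpoints. On Table 2's definitions, the SDF planning rate counts lesions that did not arrest, which is minor failure. The restoration rate is described as combined. Neither is a major-failure rate, and none appears elsewhere in the protocol text. Major failure is only one component of all failure, so its rates, and usually the difference between arms, will be smaller.

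Withdrawal at minor failure adds to the uncertainty. A child whose lesion is first found soft leaves the study before any later major failure can be seen, and this may happen to a different extent in each arm. No power figure in the plan allows for it.

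The risk lies in interpretation. A reader will take the primary comparison to have 80% power. If major failure does not differ significantly, SDF and restorations could be called comparably effective when the trial could not have shown a material difference.

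**Working it through.** **Inputs.** From Section 4.2: 29%, 63%, alpha 0.05, power 80%, 34 per group, 30% attrition. From Section 4.4: 1:1 allocation. Assumed: a two-sided test (the plan does not state sidedness) and every major-failure rate below.

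**Method.** Number per arm by the pooled two-proportion formula, with p̄ the mean of the two rates:

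n = [1.96·√(2p̄(1−p̄)) + 0.842·√(p₁(1−p₁) + p₂(1−p₂))]² / (p₁−p₂)²

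Power is by exact binomial enumeration of the uncorrected chi-square test, as an approximation to the planned mixed model.

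**Step 1: reproduce the plan's figure.** For 29% vs 63%, p̄ = 0.46. The numerator is (1.96·√0.4968 + 0.842·√0.4390)² ≈ 3.76 and the denominator is 0.34² = 0.1156, so n = 32.5, or 33 per arm. Exact power at 34 per arm is 81%. Attrition: 34/0.70 = 48.6, or 49 per arm and 98 in total. The stated numbers therefore belong to this contrast.

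**Step 2: major failure as an equal share of all failures in both arms.** Multiply 29% and 63% by the assumed share. The 49-per-arm column assumes that all 98 children are retained.

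| Share major | Rates (restoration vs SDF) | Power, 34 per arm | Power, 49 per arm | n per arm for 80% |
|---|---|---|---|---|
| 75% | 21.75% vs 47.25% | 63% | 76% | 54 |
| 50% | 14.5% vs 31.5% | 40% | 52% | 95 |
| 25% | 7.25% vs 15.75% | 21% | 28% | 220 |
| 10% | 2.9% vs 6.3% | 7% | 12% | 595 |

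**Step 3: unequal shares.**

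| Shares (restoration, SDF) | Rates | Power, 34 per arm | Power, 49 per arm |
|---|---|---|---|
| 25%, 50% | 7.25% vs 31.5% | 76% | 90% |
| 50%, 75% | 14.5% vs 47.25% | 86% | 95% |
| 50%, 25% | 14.5% vs 15.75% | 6% | 6% |

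**Step 4: no share assumption.** The SDF major-failure rate needed for 80% power, given the restoration rate:

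| Restoration rate | SDF rate, 34 per arm | SDF rate, 49 per arm |
|---|---|---|
| 5% | 29% | 23% |
| 10% | 38% | 32% |
| 14.5% | 44% | 39% |

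**Step 5: cross-check by another route.** Take restoration major-failure rates of 2% to 15% and keep the planned effect, using the normal approximation at 34 per arm. With the planned relative risk (0.63/0.29 = 2.17), power runs from 8% to 40%. With the planned odds ratio ((0.63/0.37)/(0.29/0.71) = 4.17), it runs from 20% to 71%.

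**Step 6: any failure as the alternative home for the 80%.** The 63% belongs to annual application, while Section 5.2 plans a second application at 6 months. Section 3.5's 12-month biannual figure implies 100% − 53% = 47% non-arrest. For 29% vs 47%, p̄ = 0.38 and n = (1.96·√0.4712 + 0.842·√0.4550)²/0.18² ≈ 113 per arm. Power is 35% at 34 per arm and 45% at 49.

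**The case against.** The strongest reply is that the 80% was never claimed for the major-failure model. Section 10 speaks of the power of the study and separately plans a chi-square test on failure rates, which is the kind of test for which 34 per group reproduces. Section 4.1 frames effectiveness by both major and minor criteria, and Section 6 counts a tooth with either as failed. On this reading any failure may be what was intended, and Section 10 is the outlier. This shows an inconsistency across sections. It does not give the named primary outcome 80% power, and Section 10 is explicit about which outcome is primary.

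Second, the major-failure rates are assumed, equal shares have no support in the protocol, and some unequal cases exceed 80%. That stands: no single power figure can be given. The mismatch does not depend on any of these rates.

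Third, the power figures above do not model withdrawal at minor failure either. That also stands, and a power table will not resolve it.

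Fourth, Section 4.2 does not define combined, and the nQuery output in Appendix 1 was not available for this review. Reading combined as major plus minor is an inference, supported by Table 2 citing the same source as the 29%. The stated rates do reproduce the sample size.

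Finally, the plan makes no equivalence claim, and it already reports odds ratios with 95% confidence intervals. The interval is therefore in place. What is missing is a correct power statement and a caution on reading a null result.

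**Conclusion.** The concern holds. The 80% applies to 29% combined failure against 63% non-arrest and has no stated basis for major failure. Power for the primary outcome is unknown and probably below 80%. With equal shares of 10% to 75% it is 7% to 63% at 34 per arm, and 12% to 76% even if all 98 children are retained. It could exceed 80% if major failure makes up a much larger share of failures with SDF than with restorations. These figures rest on assumed rates, a two-sided test, and a simple two-proportion comparison with no allowance for withdrawal at minor failure. The mismatch of endpoints rests on none of these. It should be corrected because it concerns the power claim for the primary analysis.

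**What to change.** Keep major failure as the primary outcome and correct the power statement.

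1. In Section 4.2, say that 34 per group gives 80% power only for 29% combined failure against 63% non-arrest.
2. In Section 10, remove 80% as a claim about the primary outcome. Add a short table of power for major failure over explicit assumed rates, for example 14.5% vs 31.5%: 40% at 34 per arm and 52% at 49. Note that it does not allow for withdrawal at minor failure.
3. State that the major-failure comparison will be read through its 95% confidence interval, and that a non-significant result is not evidence of comparable effectiveness.
4. Any failure (major or minor) by 12 months can be a prespecified secondary comparison, which would make the existing chi-square on failure rates specific. Do not describe it as having 80% power until the 63% planning rate has been reconciled with the application schedule in Section 5.2 and the figures in Section 3.5.

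The cost is wording in two sections and one small table, with no extra children or data. Leaving the primary outcome unchanged matters because the trial is unblinded and recruitment had already begun when Section 4.2 was written. The drawback is a less favourable stated power: the change corrects the claim without raising the power.

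### The analysis plan does not say how a child who leaves without a failure enters the 12-month failure proportion, so with 30% loss budgeted the estimate may be biased in either direction

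*Combined protocol and SAP*

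**What the plan says.** Section 10 defines the primary outcome as "the proportion of children reporting major failures during the 12 month follow up period". It is to be analysed with a binomial mixed model that has treatment as a fixed effect, with estimates at the end of follow-up, across follow-up, and for rate of change. Random effects, visit structure and missing-data assumption are not given. On dropout the section says only: "Chi-square tests will also be used to determine differences in dropout rates, failure rates, patient satisfaction/acceptance, and overall cost".

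Section 4.2 plans for loss by enrolling more: "To account for 30% attrition, the final number needed for the initial study will be 98". Retention is supported by phone contacts and intermediate visits (Sections 4.2 and 6), payments of up to $300 (Section 8), and standardised explanation to parents and continued follow-up after a missed intermediate visit (Section 11).

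Under Section 6, a minor or major failure leads to withdrawal, and "these teeth will be categorized as a failure". Under Section 9, a provider may move an SDF child to conventional treatment, after which the child is withdrawn and the reason recorded. No outcome is assigned to that child. No section defines the analysis set, the outcome of a failure-free child who leaves, or a sensitivity analysis for missing outcomes.

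**The concern.** Failures and non-failures are not ascertained in the same way. A failure at month 3 is final and is counted. A child who is failure-free at month 3 and then leaves has no 12-month status. If such children are dropped, early failures stay in while early non-failures go out, and the proportion is too high. If they are kept as non-failures, any later failures are missed, and it is too low.

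The comparison between arms is exposed when dropout differs by arm. That is plausible here: treatment is unblinded (Section 4.4), the provider switch exists only for SDF children (Section 9), and Section 11 foresees withdrawal over tooth darkening. A test of dropout rates does not correct the estimate. Because Section 6 withdraws every child with a failure, the test would also partly repeat the comparison of failures unless dropout is defined as leaving without one.

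**Working it through.** **The plan's own figure.** Inputs from Section 4.2: "the combined failure rate for conventional restorative techniques (e.g. compomers) is approximately 29% at one year follow-up"; "application of silver diamine fluoride has a failure rate of 63% at one year follow-up"; alpha 0.05 and power 80%, giving 68 (34 per group). Sidedness is not stated; two-sided is assumed.

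n per arm = [1.96 × √(2 × 0.46 × 0.54) + 0.842 × √(0.29 × 0.71 + 0.63 × 0.37)]² / 0.34² = 32.5, so 33. This is one fewer per arm than stated, and power at 34 is 81.8%. For attrition, 34/0.70 = 48.6, so 49 per arm and 98 in total. The 92 and 86 also reproduce (34/0.75 gives 46 per arm, 34/0.80 gives 43). The inflation restores the number of completers. It has no effect on bias.

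**Bias illustration (assumption).** Failure and dropout have constant hazards over 12 months and are independent. With 12-month failure risk F and dropout risk D, h = −ln(1 − F) and c = −ln(1 − D):

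- failures seen before leaving = h/(h + c) × [1 − exp(−(h + c))]
- failure-free leavers = c/(h + c) × [1 − exp(−(h + c))]
- failure-free completers = (1 − F)(1 − D)
- leavers excluded: failures/(failures + completers)
- leavers as non-failures: failures/all randomised

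*30% dropout in both arms.*

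- Control: h = 0.3425, c = 0.3567. Failures 24.6%, leavers 25.7%, completers 49.7%. Leavers excluded: 24.6/(24.6 + 49.7) = 33.1%.
- SDF: h = 0.9943, c = 0.3567. Failures 54.5%, leavers 19.6%, completers 25.9%. Leavers excluded: 54.5/(54.5 + 25.9) = 67.8%.

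| Overall failure, true 29% v 63% | Leavers excluded | Leavers as non-failures |
|---|---|---|
| 30% v 30% dropout | 33.1% v 67.8%; gap 34.7; OR 4.25 | 24.6% v 54.5%; gap 29.9; OR 3.67 |
| 20% v 40% dropout (assumed) | 31.5% v 69.8%; gap 38.3; OR 5.03 | 26.2% v 51.4%; gap 25.2; OR 2.98 |

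The true gap is 34.0 points (OR 4.17). If failures are seen only at the 3-, 6- and 12-month visits, excluding leavers at 30% dropout gives 31.7% v 66.4%. A time-to-event estimate that censors leavers returns 29.0% and 63.0% under the same assumptions.

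**No true difference.** With 29% in both arms and 30% dropout in both, the OR stays 1.00. With 20% v 40% dropout it is 1.17 if leavers are excluded (31.5% v 35.1%) and 0.85 if they count as non-failures (26.2% v 23.0%).

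**Major failure.** The documents give no rate, so a range is assumed, with equal true risk in both arms and 20% v 40% dropout:

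- 5%: 5.6% v 6.4% (excluded) or 4.5% v 3.9% (non-failures)
- 10%: 11.1% v 12.7% or 9.0% v 7.9%

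Arm-level shifts are about 0.5 to 3 points.

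**Extreme-case limits, overall failure, 30% dropout in both arms.**

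- Lower: every control leaver fails and no SDF leaver does: 54.5 − (24.6 + 25.7) = about +4 points.
- Upper: the reverse: (54.5 + 19.6) − 24.6 = about +49 points.

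**The dropout test.** With 49 per arm, an uncorrected chi-square at 0.05 detects 20% v 40% dropout with exact power 0.584.

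**The case against.** The trial works to prevent loss through contacts, visits, payments, standardised information and follow-up after missed visits. A reader might infer that extra enrolment and a chi-square test are its whole answer to attrition; that is true of the analysis section only. Retention lowers the loss but does not say how to analyse what remains.

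No section excludes failure-free leavers. The mixed model, with targets across follow-up, suggests visit-level data, so leavers could contribute their earlier visits under a missing-at-random assumption. That is possible but cannot be confirmed from what is written.

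A reader might also infer that the treatment comparison is certainly biased. The documents do not support that. Direction depends on a rule that is not stated, and with equal independent dropout and leavers excluded the gap moves only from 34.0 to 34.7 points. The larger distortions need either leavers counted as non-failures or unequal dropout, and the 20% v 40% split is an assumption.

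The 29% and 63% are not major-failure rates, so the larger figures should not be carried over to the primary outcome. Nor do the extreme-case limits reverse the sign in the equal-dropout illustration. Finally, withdrawal reasons are recorded (Sections 4.4 and 9), so failures and other departures can be separated from data already collected. That makes the repair easy but does not make it part of the plan.

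**Conclusion.** The concern holds as a gap in the analysis plan, not as proof of bias. The plan budgets for 30% loss, keeps failures whenever they occur, and assigns failure-free leavers no outcome or denominator.

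For overall failure, the illustrated arm-level proportions move by about 4 to 9 points with 30% dropout. The between-arm gap ranges from nearly unchanged to about 4 points too small with equal dropout, and from about 4 points too large to 9 too small with 20% v 40%. For major failure at an assumed 5% to 10%, arm-level shifts are about 0.5 to 3 points. All of this rests on constant hazards and dropout independent of failure; informative dropout could do more or less. A non-significant dropout test would not show that bias is absent.

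Two features need more than ordinary censoring. Withdrawal at minor failure ends observation of a later major failure, which is the primary outcome. Provider-initiated switches from SDF may well be related to prognosis.

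**What to change.** Change the analysis section as follows.

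- Define the analysis set, and define dropout as leaving without a failure. State that a non-significant dropout test is not evidence of no bias.
- Estimate the 12-month risk of major failure, and separately of any failure, with a discrete-time or life-table model over the 3-, 6- and 12-month visits. Censor failure-free leavers at their last examination.
- For major failure, treat withdrawal at minor failure as a competing event, or report any failure as a supporting composite. Do not handle it as ordinary censoring.
- Do not treat provider-initiated switches from SDF as uninformative censoring. Vary their outcome in one tipping-point analysis that covers all missing outcomes.
- Where consent allows, check the two clinics' charts for study-tooth failures in children who miss month 12.

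The cost is SAP wording, a little more analysis on visit data already planned, and a short chart check. The chart check may miss care given elsewhere. The main estimate relies on independent censoring, which the tipping-point analysis is there to test.
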